#### 6.7 Recruitment

It is recommended that during the development of this research protocol, the principal investigator requests the approval of the Research Ethics Committee and the Research Committee, as well as the authorization to the relevant regulatory entity, to publish or disseminate in the mass media, the invitation to participate in the study to those people who meet the eligibility criteria.

It is possible to discuss with other health professionals the opportunity for healthy subjects to be evaluated by an ophthalmologist at no cost, as well as cabinet exams that will allow the more accurate determination of their ocular clinical status by participating in a sponsored clinical research protocol. by Sophia Laboratories SA of C.V.

# 7. Methods. Assignment of the intervention

#### 7.1 Generation of the allocation sequence

The random numbers will be generated through the online tool: www.randomization.com

Two strata corresponding to the intervention groups will be used, which will be balanced for a research center. The allocation will be 1: 1.

#### 7.2 Blinding mechanism

Blinding will be performed by personnel assigned by the Clinical Operations Management of Sophia Laboratories S.A de C.V. Which will consist in the elimination of the primary label (commercial) in the case of Corneregel® and the placement of a label identical to the other interventions. Because the tube in which Corneregel® is packaged differs in the color and shape of the lid used by the PRO-

CONFIDENTIAL

167, a masking will be made in the secondary packaging which will be identical for the two interventions.

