#### 6.3 Intervention

# 6.3.1 Managed treatments

# 6.3.1.1 Treatment under study

#### PRO-167

- o Active ingredients: Dexpanthenol 5%
- o Pharmaceutical form: Ophthalmic gel.
- o Prepared by: Sophia Laboratories A.S. of V.C.
- Posology: a strip approximately 1 cm long, 4 times a day during the waking period, in the bottom of the right eye sac.
- Description of the formulation: transparent gel, free of visible particles.
- o Description of the packaging: sterile multi-dose tube, low density polyethylene polyethylene and aluminum with high density polyethylene lid.

Table 3. Quali-quantitative formulation of PRO-167

Type of agent	Amount mg/mL	Function
Dexpanthenol	50.0	Active principle (lubricant)
Boric acid	2.00	Active principle
Sodium Borate decahydrate	without showing	additive
Polysorbate 80	without showing	additive
Sorbitol	without showing	additive
Potassium chloride	without showing	additive
Sodium chloride	without showing	additive
Magnesium Chloride hexahydrate	without showing	additive
Water for the preparation of injectables c.b.p.	1.00	Vehicle

Quali-quantitative formulation of the product under investigation PRO-167. The concentration of the active principles is shown, as well as the substances that act as a buffer additive.

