#### 6.3.2 Strategies to improve adherence and procedure to monitor adherence

- 1. Each visit the research subject will return the assigned tube in order to evaluate the adherence by weigh
- 2. Direct questioning by the PI about the application of the intervention.

- 3. At the discretion of the IP, messages may be sent or reminder calls made.
- 4. Delivery of a printed chronogram specifying the date of the visit and its activities
- 5. Journal of the subject.

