#### 6.3.4.3 Return

The research subjects will return to the staff indicated by the IP in the center their treatments in visits 1 and final. The refund will be made by the research center when the sponsor indicates it. Prior to the return the research center must make a count of the assigned medication and the remaining medication, with the aim of creating an inventory which serves for the final filling of the return form of the medication.

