#### 7.4 Blinding (Masking)

The blinding will correspond to the research subject and the principal investigator. In addition, the statistical analysis will be carried out in a blinded manner for the partial and final analysis.

The masking will be done using boxes in the secondary packaging identical in the two groups. Blinding for the research subject and the researcher will be done by replacing the commercial labels in the case of the comparator in the tubes and the use of identical labels that contain the assignment number.

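### Tube lids differ in colour and shape, only box and label are masked, and no provision keeps tubes from the investigator, so the investigator's blind is at risk

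*Combined protocol and SAP*

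**What the plan says.** **Who is blinded.** Section 7.4: "The blinding will correspond to the research subject and the principal investigator". The statistical analysis is also to be done blind.

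**What differs.** Section 7.2 states that the comparator's tube "differs in the color and shape of the lid used by the PRO"-167. Section 6.3.1.1 describes the test product's container as a "sterile multi-dose tube, low density polyethylene polyethylene and aluminum with high density polyethylene lid". Section 6.3.1.2 says only that the comparator comes in a sterile multi-dose tube.

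**What is masked.** For the lid, section 7.2 offers one measure: "a masking will be made in the secondary packaging which will be identical for the two interventions". At tube level, section 7.4 relies on "replacing the commercial labels in the case of the comparator in the tubes and the use of identical labels that contain the assignment number".

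**Where the tubes go.** Section 6.3.2: "Each visit the research subject will return the assigned tube", so that adherence can be measured by weight. Section 6.3.4.3: "The research subjects will return to the staff indicated by the IP in the center their treatments in visits 1 and final". Under section 6.3.2.1 the pharmacist weighs each tube before delivery and after return. Section 6.3.4 makes the investigator or a delegate responsible for handling treatment.

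**The concern.** A box masks a tube only while it is closed. The subject has to take the tube out to use it, and the tube comes back to the centre at the visits where outcomes are recorded. At that point the difference that the sponsor has identified is open to view unless something else prevents it.

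The investigator is the more exposed of the two blinded parties. A subject sees one product. An investigator may see tubes from many subjects, would then see two kinds of lid, and could sort subjects into two groups without knowing what either lid means. Because the comparator is a marketed product, recognising its lid once would identify the arm of every subject with that lid.

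The stakes come from the decision rule. Section 8.3.1 calls the product safe and tolerable when no primary variable differs clinically or statistically from the comparator. Ratings influenced by knowledge of the arm could create a difference or hide one. Section 5.6.1 itself relies on blinding to limit evaluation bias.

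**Working it through.** The plan states no figure on this point, so the check sets its provisions side by side.

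**Step 1. Is the lid masked anywhere?** Sections 7.2 and 7.4 cover the box and the label. No section covers or replaces the lid, moves the gel to a common container, or puts an opaque sleeve on the tube.

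**Step 2. When is the lid in view?**
- Subject: 4 applications a day × 10 days = 40 planned applications (sections 1 and 6.3.1), each with the tube out of its box.
- Centre: tubes are dispensed at the baseline visit and visit 1 (section 6.3.4.1) and returned at visit 1 and the final visit (section 6.3.4.3). Planned returns are at most 24 × 2 = 48. The documents do not say whether tubes come back boxed or loose.

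**Step 3. Is the investigator kept away from tubes?**

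| Task | Who, according to the protocol | Investigator excluded? |
|---|---|---|
| Receiving shipments and checking contents (6.3.4.1) | Centre team, the researcher included | No |
| Handling treatment (6.3.4) | Investigator or delegate | No |
| Handing tubes to subjects (6.3.4.1) | Personnel chosen by the investigator | No |
| Receiving returned tubes (6.3.4.3) | Staff chosen by the investigator | No |
| Weighing (6.3.2.1) | Pharmacist | In effect, for this task |
| Judging whether a tube is damaged (6.3.2.1) | Not named | No |
| Assessing adherence (6.5.1.3) | Investigator, under 6.3.2.1 | Tube need not be seen |

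Only weighing is reserved for the pharmacist.

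**Step 4. Which primary variables does this reach?** Sections 6.4.1.1 and 6.4.1.2 list 3 + 4 = 7.
- Rated or elicited at the visit: epithelial defects (Oxford grade by direct observation, 6.4.3.4.1), adverse events (registered by the investigator, 6.4.3.5), and burning, foreign body sensation and itching (direct questioning, 6.4.3.9). That is 1 + 1 + 3 = 5.
- Completed by the subject: eye comfort index (6.4.3.3), 1.
- Taken from the histopathology report: goblet cell density (6.4.3.2), 1, and much less exposed.

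The protocol names no separate, tube-free assessor for the first five. Hyperaemia and chemosis, which are secondary, are graded in the same way.

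**Step 5. Could biased ratings change the conclusion? (Illustration on assumed rates only.)** Take 12 subjects per arm, with a and b reporting a symptom, and pooled q = (a + b)/24. The Pearson statistic is X² = [(a − b)/12]² / [q(1 − q) × 2/12], significant above 3.8415. Summing the binomial probabilities of all significant (a, b) pairs gives:

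| Recorded rates | Probability of a significant difference |
|---|---|
| 10% v 10% | 0.015 |
| 10% v 20% | 0.068 |
| 10% v 30% | 0.198 |
| 10% v 40% | 0.387 |

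Read downwards, with equal true rates of 10%: over-recording one arm by 10, 20 or 30 points raises the chance of a false difference from 0.015 to 0.068, 0.198 or 0.387. Read upwards, with a true 10% v 40%: under-recording the higher arm by 10 or 20 points lowers the chance of detection from 0.387 to 0.198 or 0.068. The table shows that the decision rule is sensitive in both directions. It does not estimate any bias in this trial.

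**The case against.** The best defence is that the tubes already have a custodian. Section 6.1.1 requires a pharmacist, and section 6.3.2.1 has the pharmacist weigh tubes before delivery and after return and record the result. The investigator's adherence assessment can rest on those weights and on the diary. The elimination criterion in section 6.2.3 uses the diary alone. An investigator could therefore meet every stated duty without seeing a tube. This stands, and it narrows the gap to delivery, receipt and inspection, where nothing keeps the investigator away. A blind should not depend on unwritten practice.

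Second, the subject's blind is under less strain than the lid difference first suggests. Each subject gets one product with a neutral label, and users of topical eye medication and contact lens wearers are excluded (section 6.2.2). Nothing suggests that these volunteers know the marketed lid. This also stands. A reader might count the subject's own ratings and infer that six of the seven primary variables are compromised. That merges a weak route with a stronger one.

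Third, a reader might take the 48 returns as 48 sightings of a lid by the investigator. The documents do not support that: they do not say that tubes come back unboxed or that the investigator is present, section 6.6.1 allows 20% for losses, and sections 6.3.2.1 and 10.5 foresee tubes not being returned. Nor is it known that one investigator would see every tube, because the number of centres is not stated.

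Finally, both arms receive 5% dexpanthenol gel with the same posology, so expectations may differ less than they would against placebo. That may reduce the bias but does not remove the route.

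**Conclusion.** The point holds as a weakness in how the investigator's blind is protected. The sponsor knows of a visible difference between the products, masks it only with box and label, and lets the investigator, or anyone the investigator names, handle, hand over and receive tubes at the visits where outcomes are rated. Five of seven primary variables are exposed by this route.

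A reader might infer that the trial is not in fact double blind. The documents do not support that: they show an opportunity for unblinding, not its occurrence. Sorting subjects requires that an assessor sees tubes from both arms, and naming the arm requires that the marketed lid is recognised. Both are assumptions.

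The only firm count is the ceiling of 48 planned returns, which assumes no losses and every tube returned. The size of any bias cannot be derived. The risk through the subject is real but lower.

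**What to change.** Amend sections 6.3.2.1, 6.3.4, 6.5.1.3 and 7.4 to state that:

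1. At the centre, only the pharmacist opens boxes and hands over, receives, inspects and weighs tubes, and passes only the adherence figure to the investigator. The reception wording in 6.3.4.1 and the return wording in 6.3.4.3 change to match. The investigator keeps overall responsibility through the existing delegation form.
2. Subjects carry and return tubes in the closed box, and do not show or describe them to the investigator.
3. Anyone who grades staining, hyperaemia or chemosis, questions subjects about symptoms, or assesses adverse events does not see a tube. It follows that the pharmacist rates no outcome.
4. If feasible, the sponsor makes the lids look alike when the comparator is relabelled. If not, the study report states that the subject-level blind is limited to label and box.

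Item 4 is conditional because the documents do not show that the lid of a multi-dose tube opened several times a day can be disguised and stay usable. Items 1 to 3 protect the assessors without it, but do not hide the lid from the subject.

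**Cost.** A few lines of protocol text and no new role, since the pharmacist is already required and already weighs the tubes. The pharmacist has slightly more work, and the investigator can no longer inspect tubes in person. Item 4, if adopted, adds a step to relabelling, whose cost the documents do not allow to be estimated. No dose, schedule or unblinding rule changes.

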#### 7.3 Implementation

The allocation sequence will be generated by personnel assigned by the Clinical Operations Management of Sophia Laboratories S.A de C.V. The research center will receive a set of envelopes which will contain the intervention number individually. The envelopes will be identical on the outside. Each of these envelopes will be shown to the participants for their election by the principal investigator or by a designated member of their team.

#### 7.4 Blinding (Masking)

The blinding will correspond to the research subject and the principal investigator. In addition, the statistical analysis will be carried out in a blinded manner for the partial and final analysis.

The masking will be done using boxes in the secondary packaging identical in the two groups. Blinding for the research subject and the researcher will be done by replacing the commercial labels in the case of the comparator in the tubes and the use of identical labels that contain the assignment number.

#### 7.4.1 Opening of blinding

Blinding may be opened in the following cases:

- 1. Presence of a serious adverse event.
- 2. Safety alarm due to the use of the drugs under study.
- 3. In case the sponsor determines it for any security reason or other reason that it considers pertinent

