#### 9.3.1.1 Record of adverse events in the Case Report Form

The registry of adverse events considers the information concerning the identification data of the participating patient as code, age, sex, left eye, right eye.

Information about the type of adverse event, adverse reaction or suspected adverse reaction to the product under investigation or to the study medication, as appropriate. The date on which the adverse event occurs is reported, as well as in which the Investigator is aware of it, date of resolution or outcome, as applicable. The clinical diagnosis is indicated. Include in concomitant medications the therapy used for the pharmacological management of the adverse event, suspected adverse reaction, adverse reaction. Record the outcome or resolution of the event: patient recovered without sequelae, with sequelae, not recovered. Patient who presented death due to adverse reaction / adverse event, patient who presented death and it is judged that the drug could have contributed, patient who presented death and this is not related to the investigational product or drug, or indicate that it was not He knows what the consequence of the event is.

Consign information about the product or drug under investigation or the drug associated with the adverse event, adverse reaction or suspected adverse reaction. As applicable, information concerning generic denomination, distinctive denomination or product code in research and / or investigational medication should be recorded, as appropriate according to the methodological design of the study, this is relevant in the case of blinded studies or those where they use placebo as comparators, since there are circumstances that justify opening the cecum to determine if the adverse event, the adverse reaction or suspected adverse reaction may be attributable to the active agent, the combination of active agents, or the substance (s). s) pharmacologically inert (s), such as vehicles or additives, as appropriate the phase of clinical research in which the development of the drug is located. It will also be necessary to record the data concerning the batch number, manufacturer laboratory, expiration date, dosage, route of administration, start and end dates of administration and / or consumption, reason for the prescription; according to whether it is a Sophia Laboratories A.S. of V.C.

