IV	The causal relationship is doubtful	0

The reagents considered by the algorithm of Karch and Lasagna modified by Naranjo where each one receives a defined score are shown and the final summation allows estimating the probabilistic category of the cause-effect relationship between the administration of the drug / product in research / investigational medicine and the adverse reaction, adverse event or suspected adverse reaction. Consider that if the information is not available, a score equal to zero is recorded.

Table 6. Algorithm of Karch and Lasagna modified by Naranjo

In such a way that the degree of certainty to establish the investigational product or investigational medication (as appropriate) as the causal agent of the harmful phenomenon that befalls the participating patient, can be directly indicated by the principal investigator based on his or her clinical experience or well through the voluntary application of the tool mentioned previously. However, it is important that the researcher take into account the following arguments in favor of the causal relationship:

- a) Force of association that refers to the number of cases in relation to those exposed.
- b) The consistency of the data, ie the presence of a common characteristic or pattern.
- c) The exposure-effect pattern: which determines the relationship with the site of onset, time, dose and reversibility after suppression.
- d) The biological plausibility: which refers to the possible pharmacological or physiopathological mechanisms involved in the development or presentation of the adverse event.
  - e) Experimental findings: for example the appearance of anomalous metabolites or high levels of drug or the product of its biotransformation.
  - f) Analogy: experience acquired with other related drugs, adverse reactions frequently produced by the same family of pharmacological agents.
  - g) Nature and characteristics of the data: objectivity, accuracy and validity of the relevant documentation. [49]

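### Section 7.4.1 lets the sponsor open the blind for any reason it finds pertinent, with no limit on timing or scope and no barrier to analysts or decision-makers, so the blinding promised in 7.4 and 8.3.1 can be bypassed

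*Combined protocol and SAP*

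**What the plan says.** Section 7.4 states who is blinded: "The blinding will correspond to the research subject and the principal investigator". It adds that "the statistical analysis will be carried out in a blinded manner for the partial and final analysis". Section 8.3.1 repeats that the sponsor's analysts do not know the groups and says the groups are coded by number.

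Section 7.4.1 then lists when the blind may be opened:

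- Ground 1 is triggered by a single clinical fact: "Presence of a serious adverse event".
- Ground 2 is broader and is not defined further: "Safety alarm due to the use of the drugs under study".
- Ground 3 is left to the sponsor's own decision: "In case the sponsor determines it for any security reason or other reason that it considers pertinent".

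It does not say who opens the code under grounds 1 and 2, whether one subject or the whole list is revealed, who is told, or how an opening is documented.

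On attribution, section 9.3.1.1 says that in blinded studies "there are circumstances that justify opening the cecum to determine if the adverse event" stems from the drug itself or from inactive ingredients (the odd noun is evidently a mistranslation of blind). Section 9.3.1.4 says the degree of certainty about causality "can be directly indicated by the principal investigator based on his or her clinical experience"; voluntary use of an algorithm is the alternative.

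**The concern.** Ground 3 is a stated rule, not a missing detail. Its second half gives the sponsor an open discretion that need have nothing to do with safety. The sponsor makes PRO-167, generates the sequence, queries the data, analyses them, judges the partial analysis and writes the report.

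Under section 8.3.1 the product is declared safe and tolerable when no primary variable shows a clinical or a statistical difference from the comparator. The plan does not define a clinical difference, so that half of the criterion is a judgement, and knowing which arm is which can sway it. The same knowledge could influence which data are queried before freeze. If the right were used, the trial could still be reported as double blind with no record of the opening.

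A second, smaller issue is that a serious event's relation to the product may be rated by an investigator who already knows the product.

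**Working it through.** The plan gives no figure on this point, so the check is a comparison of sections.

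**Limits on ground 3**

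- Reason: safety, or anything else the sponsor finds pertinent. The second alternative has no boundary.
- Timing: section 8.2 has the sponsor's Scientific Committee give the last review and set the database freeze. No section links unblinding to that freeze.
- Scope: one subject, one arm and the whole list are all permitted.
- Recipients and record: no section addresses either.

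**Who holds the discretion and who handles the data**

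| Task | Responsible | Section |
|---|---|---|
| Masking of the tubes | Staff assigned by Clinical Operations Management | 7.2 |
| Allocation sequence | Staff assigned by Clinical Operations Management | 7.3 |
| Data queries, including after transfer to the spreadsheet | Sponsor staff | 8.1 |
| Database freeze | Sponsor's Scientific Committee | 8.2 |
| Statistical analysis | Sponsor staff, stated to be blinded | 8.3.1 |
| Partial evaluation and the study's fate | Clinical Operations and Medical Management | 9.2 |
| Final report | Scientific Committee of Clinical Operations | 10.10.1 |

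Sections 7.4 and 8.3.1 say the analysts are blinded. Nothing says that the result of a 7.4.1 opening must be withheld from them or from the managers in 9.2.

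**From one opening to both arms**

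There are two groups of 12 (section 6.6), 24 subjects in all. I read the coding sentence in 8.3.1 as one number per group. A person who sees the coded data and learns one subject's product then knows what that subject's group number stands for. With only two groups, the other number is known by elimination. One disclosure therefore decodes 12 + 12 = 24 records in the coded data set. If the coding sentence means something else, this step fails, but the lack of a barrier remains.

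**Where the causality rating goes**

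- The investigator records seriousness, intensity and relation to the product (9.3.1.3, step E).
- Ground 1 allows opening when a serious event is present, with no test of whether care depends on knowing the product. Section 9.3.1.1 foresees opening in order to settle attribution. No section sets an order between the rating and the opening.
- The primary safety variable is the presence of adverse events (6.4.1.1), measured in Table 4 as a count and as present or absent. Relatedness does not enter it.
- The early-termination rule in 9.2 counts serious events by group, also without regard to relatedness.
- Relatedness does decide whether the sponsor pays for the subject's care (9.3.1.3, step D; 9.3.2).

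An open rating can thus change the attribution of that event and what follows from it, but not the primary comparison.

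**The case against.** The fairest defence is that 7.4.1 is an exception inside 7.4, that blinded analysts and coded groups are promised, that the partial analysis is itself described as blinded (6.5.2), and that this is a small exploratory phase I trial. On this view 7.4.1 needs only a clarification of who opens the code and how it is recorded. The first part stands: an exception is not a contradiction, and the analysis is not without protection. It does not answer ground 3, because a promise of blinding does not bind a sponsor that has reserved the right to set it aside for non-safety reasons.

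A reader might also infer several stronger things that the documents do not support:

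- *That the sponsor may open the blind for any serious event.* Only ground 3 names the sponsor.
- *That the blind is opened before causality is rated.* The text permits this but does not prescribe it, and 9.3.1.1 is general wording about what to record.
- *That biased causality ratings would distort the primary endpoint.* They do not enter it. A serious event is also an elimination criterion (6.2.3), so opening that subject's code has little bearing on that subject's later assessments.
- *That a probability of unblinding can be given.* The documents state no serious-event rate, and ground 1 says the blind may be opened, not that it will be. A chance of at least one serious event is not a chance of an opening.
- *That one opened code reveals all allocations at the site, because the comparator's tube* "differs in the color and shape of the lid" *from the PRO-167 tube.* That is a separate masking weakness in 7.2 which exists without 7.4.1, and a full disclosure assumes that the person told also sees every tube.

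**Conclusion.** The concern holds in a limited form. Ground 3 gives the sponsor an unrestricted power to unblind, and no stated barrier separates an opened code from analysts or decision-makers, so the safeguards in 7.4 and 8.3.1 can be bypassed. At worst, one disclosure decodes both arms of 12, assuming one code number per group and access to the coded data. How often the power would be used cannot be estimated from the documents, and nothing suggests an intention to use it. The causality issue is secondary and confined to the attribution of a serious event. The change is worth making because ground 3 is an explicit rule, its non-safety half is not needed to protect subjects, and the remedy is nearly free.

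**What to change.** In section 7.4.1, with a matching sentence in 9.3.1.1:

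1. Delete the second alternative in ground 3, so that only safety reasons remain.
2. Before the database freeze in 8.2, limit any opening to the single subject whose safety requires it, or for whom an authority demands it. This excludes opening a whole group before freeze.
3. Record seriousness, intensity and causality before the code is opened where feasible, with an explicit exception for emergencies.
4. Disclose the result only to those who need it for that subject's safety, including the treating investigator, and to pharmacovigilance. Withhold it from analysts and from those who judge the group comparison, including those in charge of the partial evaluation in 9.2.
5. Document each opening and list all of them in the final report.

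The cost is a few sentences, and the sponsor gives up a discretionary non-safety right to unblind. Access for safety is kept. The change does not remove the sponsor's practical access to the sequence, which its own staff generate under 7.3; it makes use of that access outside the rule a reportable deviation.
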